7. SAFETY REPORTING

7.1 Section 10 WMO event

In accordance to section 10, subsection 1, of the WMO, the investigator will inform the subjects and the reviewing accredited METC if anything occurs, on the basis of which it appears that the disadvantages of participation may be significantly greater than was foreseen in the research proposal. The study will be suspended pending further review by the accredited METC, except insofar as suspension would jeopardize the subjects' health. The investigator will take care that all subjects are kept informed.

7.2 AEs, SAEs, and SUSARs

Adverse Events Adverse events are defined as any undesirable experience occurring to a subject during the study, whether or not considered related to the study procedures. All adverse events reported spontaneously by the subject or observed by the investigator or his staff will be recorded.

- Serious Adverse Events A serious adverse event is any untoward medical occurrence or effect that
- results in death;

- is life threatening (at the time of the event);
- requires hospitalisation or prolongation of existing in patients' hospitalisation;
- results in persistent or significant disability or incapacity;
- any other important medical event that did not result in any of the outcomes listed above due to medical or surgical intervention but could have been based upon appropriate judgement by the investigator.

An elective hospital admission will not be considered as a serious adverse event. AEs and SAEs will be reported by the treating physician in the electronic medical patient file. The investigator will report all SAEs to the sponsor without undue delay after obtaining knowledge of the events.

The sponsor will report the SAEs through the web portal ToetsingOnline to the accredited METC that approved the protocol, within 7 days of first knowledge for SAEs that result in death or are life threatening followed by a period of maximum of 8 days to complete the initial preliminary report. All other SAEs will be reported within a period of maximum 15 days after the sponsor has first knowledge of the serious adverse events.

- Suspected Unexpected Serious Adverse Reactions Adverse reactions are all untoward and unintended responses to an investigational product related to any dose administered.

Unexpected adverse reactions are SUSARs if the following three conditions are met:

1. the event must be serious;
2. there must be a certain degree of probability that the event is a harmful and an undesirable reaction to the study procedure
3. the adverse reaction must be unexpected, that is to say, the nature and severity of the adverse reaction are not in agreement with the product information as recorded in:
 - Summary of Product Characteristics (SPC) for an authorised medicinal product;

7.3 Unexpected findings

In case of an unexpected findings, the participant will be informed. In the informed consent the participant is also asked for permission to share any unsuspected findings with his/her general practitioner.

8. STATISTICAL ANALYSIS

Descriptive statistics will be performed. New onset cognitive impairment and dementia will be determined (according to the MMSE scale) and compared between CAA-related and HA-related ICH. Prevalence of different biomarkers in CSF and MRI and their evolution over time will be assessed. Linear regression analysis will be used to examine associations of MRI and CSF markers primarily with the MMSE and secondarily with the other cognitive scores. Some MRI markers, such as MB's count will be transferred logarithmically. Based on our power calculation (see references paragraph 5.4) we expect that the number of participants will be sufficient for analyses of difference in cognitive decline between CAA-related ICH and HA-related ICH. This pilot study is, however, not powered to detect significant associations between cognitive decline, MRI markers and CSF markers. The

evolution of MRI and CSF markers will, however, give enough insight to power a larger trial to investigate the underlying mechanisms of cognitive decline after ICH. In addition, we will assess whether levels of MRI and CSF markers change between 6 and 12 months after the ICH to decide which timepoint is most relevant for a larger study as in the subsequent study we aim to have one follow-up time point for a MRI and lumbar puncture.

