Methods: Data will be collected at four measuring points: at baseline (during hospital admission for the ICH or at the outpatients clinic within one month of presentation with an acute ICH), after three months, after six months and after 12 months. Premorbid cognitive functioning will be assessed with the Informant Questionnaire on Cognitive Decline in the Elderly (IQCODE) to select participants without pre-existing cognitive impairment.

At baseline, the premorbid functional status will be assessed with the modified Rankin Scale (mRS) and Barthell index. A 3Tesla MRI will be performed to assess the most likely underlying cause of the ICH (patients with either CAA or HA-related ICH will be included). Stroke severity will be assessed with the National Institutes of Health Stroke Scale (NIHSS) and a neurologic exam will be performed. Participants will undergo an extensive interview on life-style, vascular risk factors and medication, and

will undergo a blood withdrawal. Neuropsychological testing will be performed and questionnaires will be used for screening for depression, anxiety and psychopathology. In addition, participants will be asked to undergo a lumbar puncture to collect cerebrospinal fluid (CSF).

After three months, neurological examination, and neuropsychological testing will be repeated.

After six and 12 months, the neurological examination, the 3 Tesla MRI and neuropsychological testing will be repeated. Additionally, participants will be asked for a lumbar puncture at these two time points.

Main study parameters/endpoints: The main parameters are cognitive decline (according to the neuropsychological assessment) at 12 months. Secondary outcomes are burden of SVD markers on MRI and CSF markers at baseline, at six months and 12 months.

Nature and extent of the burden and risk associated with participation, benefit and group relatedness: The risks of MRI are minimal (risk of everyday life), because there are no consequences to the health of the participant. Contra-indications will be carefully investigated per subject, burden will be kept at a minimum by using short protocols. There is no direct benefit for the patients except for more insight into the underlying pathophysiology of the hemorrhages related to their disease.

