The incidence of new-onset dementia after stroke has been addressed in a cohort of 218 ICH patients. In these ICH survivors without dementia at baseline, new-onset dementia occurred with an incidence of 14.2% at 1 year and 28.3% at 4 years of follow up. Interestingly, this incidence was twice as high in patients with lobar ICH (23.4% at one year follow-up) than for patients with non-lobar ICH (9.2% at one year follow-up). This finding is in line with previous studies linking CAA to cognitive impairment.⁶

MRI markers and cognitive impairment

Underlying SVD-related pathology can be identified using MRI. Even though MRI does not show the entire spectrum of the underlying SVD pathology, it has improved our understanding of SVD pathology extensively in the recent years.⁷ MRI markers associated with CAA often are different or have a different distribution compared with MRI markers associated with HA.⁸ Deep cerebral microbleeds (MB's), white matter hyperintensity (WMH), and MRI visible enlarged perivascular spaces (ePVS) located in the area of the basal ganglia are associated with HA.⁹ Markers associated with CAA include lobar MB's, WMH, ePVS in the subcortical white matter, cortical subarachnoid hemorrhage (cSAH), intragyral hemorrhages, microinfarcts, cortical thinning, and cortical superficial siderosis (cSS).⁴

Severe WMH, lacunar infarcts, microinfarcts, have been associated with vascular cognitive impairment.¹⁰ The association between cognitive impairment and MB's has also been well established,¹¹ and recent studies have shown that cSS plays an important role in predicting progression of CAA.^{12, 13} Additionally, altered white matter integrity measured with diffusion tensor imaging (DTI) has been found in patients with mild cognitive impairment¹⁴ and CAA¹⁵ and might be a marker of cognitive decline in post-ICH patients.

As both HA and CAA are likely to progress over time, and therefore continue to damage the brain, it can be assumed that these two forms of SVD cause further cognitive deterioration after ICH and that this can be demonstrated by progression of the burden of MRI markers.

Biomarkers in cerebrospinal fluid

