5.4 Sample size calculations

For this pilot study, we require 32 participants (16 CAA-related ICH and 16 HT-related ICH). This sample size is considered to be sufficient to study the feasibility of the study procedures. Furthermore, the results of a pilot study with this sample size should provide sufficient data that are needed to determine a sample size of a future, larger cohort study.

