6. METHODS

6.1 Study parameters/endpoints

Cognitive functioning

The neuropsychological assessment will consist of a battery of tests that measure different cognitive domains. Premorbid cognitive functioning will be assessed with the Informant Questionnaire on Cognitive Decline in the Elderly (IQCODE). Cognitive functioning will be tested using a Mini-Mental State Examination (MMSE), a Montreal Cognitive Assessment (MOCA), a Frontal Assessment Battery (FAB), Digit Span Test (DST), RAVLT-15 words test, Stroop test, Trail making test, the Hospital Anxiety and Depression Scale (HADS), the Center for Epidemiologic Studies Depression Scale (CES-D), the Neuropsychiatric Inventory Questionnaire (NPI-Q), the Starkstein Apathy Scale (SAS) and the Prikkelbaarheidsschaal (PS). Cognitive impairment was defined as a score ≤ 1.5 standard deviation below the general population mean in one or more cognitive domains.

MRI markers

The presence and number of MBs, cSS, WMH, cSAH, ePVS, microinfarcts, intragyral hemorrhages, cortical atrophy and other new and known small vessel biomarkers will be assessed on 3T and scored according to the STRIVE criteria.²⁰ White matter integrity will be assessed using quantitative MR measurements and perfusion will be assessed.

Biomarkers in blood and CSF

Blood samples will be analyzed for coagulation profiles, cholesterol levels, APOE status, inflammation profile and hormone levels. In addition, extra blood will be stored in the LUMC Biobank sCAA Neurological Diseases for future biomarker studies. Concentrations of A β 40, A β 42, t-tau, and p-tau181 will be measured in CSF and other biomarkers that may be identified in the future.

Other study parameters

Further parameters of this study will include demographic data, current medical conditions, vascular risk factors (including smoking, alcohol use, drugs, physical exercise, sleep, hypertension, hypercholesterolemia, diabetes mellitus, family history and medication; in women also information on female medical history such as number of pregnancies, menstruation cycle and menopause will be retrieved), neurologic history (including previous ischemic or hemorrhagic stroke), BMI, and blood pressure.

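### Section 8 specifies the CAA–HA comparison of the main outcome only as a yes/no status; a comparison on the full cognitive scores, already collected, should be added beside it

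*Protocol*

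**What the plan says.** The summary (section 1) names the main outcome: "The main parameters are cognitive decline (according to the neuropsychological assessment) at 12 months". Section 6.1 lists the tests, most of them numeric scales, and gives a threshold: "Cognitive impairment was defined as a score ≤ 1.5 standard deviation below the general population mean in one or more cognitive domains". Section 6.2 schedules the testing at baseline and at 3, 6 and 12 months.

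Section 8 states the group contrast: "New onset cognitive impairment and dementia will be determined (according to the MMSE scale) and compared between CAA-related and HA-related ICH". It names no test and no cut-off for it. The MMSE and the other scores appear there as full-scale outcomes only in the linear regressions on MRI and CSF markers. A later sentence adds: "we expect that the number of participants will be sufficient for analyses of difference in cognitive decline between CAA-related ICH and HA-related ICH". That sentence names no score, model or test.

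On size, section 5.4 says "we require 32 participants (16 CAA-related ICH and 16 HT-related ICH") and justifies this by feasibility: "This sample size is considered to be sufficient to study the feasibility of the study procedures". Objective 1 in section 3 is itself a proportion, that of new-onset dementia in each group.

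**The concern.** New-onset impairment or dementia, whether read from the MMSE or from the 1.5 SD rule, is a cut of a numeric score. A cut records which side of a line a patient falls on and discards how far cognition has moved. At 16 per group that leaves about five expected events in total.

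The CAA–HA difference is the one contrast for which section 8 expects the sample to be sufficient, and the pilot is meant to supply the inputs for a larger cohort. If the groups are compared only on status, the pilot yields a difference in proportions with a very wide interval. It yields no planned estimate of the score difference or its SD, which a cohort sized on a score would need. The protocol already treats the same scores as continuous for the markers and gives no reason for treating the group contrast differently.

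**Working it through.** **The plan's own figure.** The 32 cannot be reproduced as a power result. Section 8 writes "Based on our power calculation (see references paragraph 5.4) we expect that the number of participants will be sufficient", but section 5.4 gives no effect, level, power or test.

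**Inputs**
- n = 16 per group (section 5.4). Withdrawals and deaths are replaced (section 6.4), so 16 is taken as analysed.
- Rates at one year, the only group rates in the document (section 2): "this incidence was twice as high in patients with lobar ICH (23.4% at one year follow-up) than for patients with non-lobar ICH (9.2"%). These are dementia rates by haemorrhage site and stand in for CAA and HA.
- Level: not stated. Two-sided 5% is assumed.
- SD or mean difference on any score: not stated. It is derived below under an assumption.

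**1. Yes/no comparison**
- Expected events: 16 × 0.234 = 3.7 and 16 × 0.092 = 1.5.
- Power is the sum of Bin(a; 16, 0.234) × Bin(b; 16, 0.092) over all tables (a, b) that the test rejects: Fisher exact **8.9%**, Boschloo 17.3%, uncorrected chi-square **18.3%**.
- Precision: SE = √[(0.234 × 0.766 + 0.092 × 0.908)/16] = 0.128, so the 14.2-point difference carries roughly ±25 points (1.96 × 0.128).

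**2. The same, with commoner events.** The compared status also includes milder impairment, for which no rate is given. Taking 20–50% in HA, with CAA shifted by the same amount as in step 3 (41–73%), power is 13–16% by Fisher and 26–27% by chi-square (24–26% by the normal approximation). The overall range is about 13–27%.

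**3. Full score, if the whole distribution shifts (assumption)**
- Suppose both rates are tails of normal scores with equal SD below one cut. Then d = z(0.234) − z(0.092) = −0.726 + 1.329 = 0.603 SD.
- Noncentrality = 0.603 × √(16/2) = 1.705; with 30 degrees of freedom the critical t is 2.042; power is **37.9%**.
- Simulated integer MMSE scores capped at 30 (assumed SD 3–4): t-test 34–38%, Mann–Whitney 34–35%.
- The 95% CI half-width is 2.042 × √(2/16) = 0.72 SD.

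**4. Full score, if only a subgroup drops (assumption).** Let 23.4% of CAA and 9.2% of HA patients fall abruptly while the rest do not move. Simulated power is 9% (t) and 8% (Mann–Whitney) for a 2 SD fall, and 12% and 9–10% for a 3 SD fall. Against 9–18% in step 1, that is no clear gain.

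**5. Adjusting for an earlier score.** With earlier–later correlation r and CAA lower by b SD at the earlier visit, the standardised effect is (0.603 − r·b)/√(1 − r²), tested on 29 degrees of freedom.

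| b | r = 0.5 | r = 0.7 |
|---|---|---|
| 0 | 48% | 64% |
| 0.3 | 30% | 32% |
| 0.6 | 16% | 11% |

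Adjustment helps if the groups start equal. It falls below the unadjusted 38% if CAA already starts 0.3 SD lower.

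**6. Size for 80% power, under the shift in step 3 only**
- Proportions, with mean rate 0.163: [1.96√(2 × 0.163 × 0.837) + 0.842√(0.234 × 0.766 + 0.092 × 0.908)]² / 0.142² = 105.03, so 106 per group.
- Score: 2 × (1.96 + 0.842)² / 0.603² = 43.2, so 44 per group, or 45 with the t correction.

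**The case against.** The strongest reply is that the proportion is what objective 1 asks for, so comparing proportions is no error. That stands: the comparison should remain.

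Second, a reader might infer that the protocol rules out a score comparison. It does not. The phrase about analyses of the difference in cognitive decline is plural and open, and an analysis plan that is not shown may specify one. What stands is narrower: the only outcome form that section 8 gives for this contrast is a status, and it assigns the scores to another purpose.

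Third, a reader might take the rise from 9–18% to 34–38% as a property of the design. It depends on a common shift that the protocol neither states nor quantifies. Section 2 can be read both ways. It expects both diseases to progress and keep damaging the brain, which suits a graded shift. It also says that some survivors decline progressively while early deficits may partly resolve, which suits a subgroup. The 9% end also reflects Fisher's conservatism.

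Fourth, adjusting for an earlier score might seem to bring power to 48–64%. That needs equal earlier scores. The groups are not randomised, they differ in haemorrhage site, and section 2 says early deficits depend on site and volume.

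Finally, this is a pilot sized for feasibility, so low power alone is no defect. That is fair, but section 8 itself expects sufficiency for this contrast and wants results that can size a larger study.

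**Conclusion.** The point holds as a matter of efficiency, not validity. Section 8 specifies the CAA–HA comparison of the main outcome only as new-onset status, and the full scores have no stated role in it.

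At 16 per group and an assumed two-sided 5% level, the status comparison has about 9–18% power on the proxy dementia rates, or about 13–27% if impairment is commoner. A full-score comparison has about 34–38% if the whole distribution shifts by 0.60 SD, and no clear advantage if only a subgroup drops.

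The full score does not rescue the sufficiency statement. At 34–38% power, 62–66% of such studies would still be non-significant. That statement, and the power calculation it cites but section 5.4 lacks, is a separate matter that this change does not cure. Nor does the protocol say that the later cohort will be sized on the cut; the gap between 106 and 45 per group shows only what is at stake if it were and the shift model held.

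**What to change.** In section 8:
- Add a full-score CAA–HA comparison of 12-month cognition: the mean z-score of the cognitive tests, with the mood, apathy, irritability and other symptom scales left out, and the MMSE total as support. Report the mean difference with its 95% CI and SD, and add a rank-based check because of the MMSE ceiling.
- Keep the comparison of new-onset impairment and dementia proportions for objective 1, with exact confidence intervals.
- Use the score difference, its SD and the proportions together to size the larger cohort.
- Report change from, or adjustment for, a named earlier visit only as a sensitivity analysis, and claim no power gain from it.

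The cost is some wording and one more analysis, with no new data, visits or patients. The small downside is that a score difference is less directly clinical than a proportion, which is one more reason to report both.

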Although the implications of MRI markers in CAA and HA patients become increasingly clear, it is unknown in what way disease progression and changes in cerebrospinal fluid (CSF) show a correlation. In the hereditary form of CAA, decreasing CSF levels of A β occur before patients develop an ICH, implicating vascular deposition of A β species as early steps in CAA pathogenesis.¹⁶ Whether they have a predictive value, however, for cognitive decline after ICH remains unclear.

Potential risk factors that might affect cognitive decline after ICH

Factors like hyperglycemia, obesity, insulin resistance, and hypertension cause microvascular dysfunction and are therefore associated with cognitive impairment.¹⁷ In order to investigate the effect of SVD on cognition it is important to assess these risk factors, as well as medication use.

Implications on clinical practice

Currently no therapies to prevent or slow down cognitive impairment after stroke exist. However, understanding the underlying cause and the natural disease course might help physicians to inform patients and screen for cognitive decline in patients who are at risk. Furthermore, identifying markers that correlate with cognitive decline might be important for future therapeutic trials. The results of this pilot study will be used to power a larger cohort study to investigate underlying mechanisms of cognitive decline after ICH and the differences between non-CAA and CAA related pathology. We will learn about the prevalence of cognitive decline, the differences between markers and their association with cognitive decline and the optimal time points for MRI (6 or 12 months) to assess the potential of creating a prediction model of the SVD markers and cognitive decline.

Overall aim: The overall aim is to study cognitive decline in patients who recover from ICH and the relation with SVD markers. The results will be used to design a larger cohort study.

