3. OBJECTIVES

1. To investigate the proportion of patients with new-onset dementia after HA-related ICH and CAA-related ICH by performing serial follow-up with neuropsychological testing.
2. To investigate MRI markers for SVD disease at baseline and their progression during follow-up and study if and how these markers correlate with cognitive decline after HA-related ICH versus CAA-related ICH.
3. To assess CSF markers at baseline and progression during follow-up and study if and how CSF markers correlate with cognitive decline after HA-related ICH versus CAA-related ICH.
4. To store blood and CSF of CAA and HA patients for biobanking purposes and future research.

The results from this pilot study will be used to design a larger cohort study to investigate underlying mechanisms of cognitive decline after ICH.

The cognitive decline and influencing factors ICH patients will be (whenever appropriate and dependent on the particular research question) compared with data from other research projects in the LUMC like the hereditary form of CAA (HCHWA-D, n=75), sporadic CAA (n=50), Alzheimer's disease, and Huntington's disease or available data on healthy controls.

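### The only stated marker regression uses cognitive scores, with no earlier score and no CAA/HA split, so as written it does not answer objectives 2 and 3 on decline after HA- versus CAA-related ICH

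*Protocol*

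**What the plan says.** Section 1 (Summary) sets the endpoint: "The main parameters are cognitive decline (according to the neuropsychological assessment) at 12 months". Section 3 (Objectives) asks of the MRI markers to "study if and how these markers correlate with cognitive decline after HA-related ICH versus CAA-related ICH", and of the CSF markers to "study if and how CSF markers correlate with cognitive decline after HA-related ICH versus CAA-related ICH". Both objectives also cover how the markers progress during follow-up.

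Section 8 (Statistical analysis) states one model for the markers: "Linear regression analysis will be used to examine associations of MRI and CSF markers primarily with the MMSE", and then with the remaining cognitive scores. No visit, change score, earlier score, group term or stratification is named. The same paragraph does set a group contrast for new-onset impairment and dementia, which are to be "compared between CAA-related and HA-related ICH". The evolution of markers is to be assessed, but that sentence links it neither to cognition nor to group. The study is declared "not powered to detect significant associations between cognitive decline, MRI markers and CSF markers".

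Section 2 says that the pilot should teach about "the differences between markers and their association with cognitive decline" and help to assess "the potential of creating a prediction model of the SVD markers and cognitive decline".

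**The concern.** The objectives fix two features of the marker question: the outcome is decline, and the association is to be contrasted between the two diseases. The model sentence has neither.

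A score at one visit is not decline. By the protocol's own account in section 2, part of the early deficit comes directly from the haemorrhage and may later partly resolve. A score also carries ordinary differences in premorbid ability. A marker can therefore track the score without tracking decline, or the reverse.

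A single fit over all 32 patients also cannot show whether an association differs between CAA and HA. Lobar microbleeds and cortical superficial siderosis are part of the definition of probable CAA in Appendix A, so for these a pooled association may partly re-express the diagnosis. This does not extend to every marker, since section 2 links white matter hyperintensities, perivascular spaces and microbleeds to both diseases.

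At stake is whether the pilot delivers the marker estimates that its successor is meant to draw on.

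**Working it through.** **Text comparison.** The finding rests on this and needs no arithmetic.

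| Feature | Objectives 2 and 3 | Section 8 marker model |
|---|---|---|
| Outcome | cognitive decline | MMSE, then other scores |
| HA versus CAA | asked for | not named |
| Marker | baseline and progression | not stated |

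The data for a decline analysis exist: section 6.2 has neuropsychological testing at baseline, 3, 6 and 12 months.

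**Illustration 1: level against adjusted score (assumed inputs).** In units of the premorbid SD, take acute effect SD 0.6, decline SD 0.5, half the acute effect recovered by month 3 and none later, test noise SD 0.45.
- Variance of the 12-month score: 1 + 0.25×0.36 + 0.25 + 0.2025 = 1.5425. Correlation with decline: 0.5/√1.5425 = 0.40.
- Adjusted for baseline: baseline variance 1 + 0.36 + 0.2025 = 1.5625; covariance 1 + 0.5×0.36 = 1.18; residual variance 1.5425 − 1.18²/1.5625 = 0.651; correlation 0.5/√0.651 = 0.62.
- Adjusted for month 3: 0.63 if no decline occurs before month 3, and 0.54 if a quarter of it does.

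The range was 72 scenarios: acute SD 0.3, 0.6 or 1.0; decline SD 0.3 or 0.5; recovery by month 3 of 0.3, 0.5 or 0.7; later recovery 0 or 0.2; early decline 0 or 25%. The score alone gives about 0.22 to 0.41 and the adjusted score 0.35 to 0.63, a ratio of 1.27 to 1.95. Which reference score is better depends on recovery timing that the documents do not give.

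**Illustration 2: pooling the groups (assumed inputs).** Take a marker with no within-group effect. The groups differ by d SD in the marker and g SD in the score. Then pooled r = (dg/4)/√[(1+d²/4)(1+g²/4)]. The SE at n = 32 is 1/√29 = 0.186 on the Fisher scale.
- d = 1, g = 0.3: r = 0.07, or 0.36 SE
- d = 1.5, g = 0.5: r = 0.15, or 0.79 SE
- d = 2, g = 0.8: r = 0.26, or 1.45 SE

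If instead the standardised slopes were −0.5 in CAA and 0 in HA with equal marker spread, one common slope would be −0.25 and describe neither group.

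**Precision of a model that fits the objectives.** Section 5.4 gives 16 + 16 patients; complete data are assumed.
- Residual df: marker only 32 − 2 = 30; with earlier score and group 32 − 4 = 28; within one group with earlier score 16 − 3 = 13; with marker × group added 32 − 5 = 27.
- Common slope: (2.048/2.042)×√(30/28) = 1.04, so intervals about 4% wider.
- Group term: the SE grows by √(1+d²/4), which is 1.12 at d = 1 and 1.41 at d = 2.
- Within-group slope against common slope, equal marker spread: √2×2.160/2.048 = 1.49.
- Difference between the two slopes: SE √(1/16+1/16)/√(1/32) = 2 times that of the common slope.
- A partial r of 0.30 has a 95% CI of −0.07 to 0.60 overall (Fisher SE 1/√27) and −0.25 to 0.70 within a group (1/√12).

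**The case against.** The strongest reply is that the sentence is silent rather than wrong. Covariates, stratification and interactions are commonly left to an analysis plan, and one may exist. Nothing in section 8 says that the groups will be pooled or that the outcome is a single level. Its later remark on power speaks of associations with cognitive decline, so the MMSE may simply name the instrument. An analysis plan could supply change and group without contradicting the protocol.

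Much of this stands. The missing covariate list is no finding, and the sentence is compatible with a decline analysis. What remains is that the one stated model lacks both features that the objectives ask for, while the same paragraph spells out the group contrast for impairment and dementia. The remark on power neither defines decline nor adds a contrast.

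A reader might also infer that the regression would produce false-positive markers. The documents do not support that. Such results need an assumed correlation of the marker with the baseline score, or assumed group differences in both marker and outcome, and the documents give none of these. The pooling artefact in illustration 2 is mostly within sampling error at n = 32. No decision rule depends on this regression, and section 8 rests the powering of the larger study mainly on marker evolution.

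**Conclusion.** The point holds as a mismatch within the protocol, and as an improvement to consider rather than an error that invalidates the study. Followed as written, section 8 gives a pooled association with a score level and leaves the decline and HA-versus-CAA parts of objectives 2 and 3 unanswered. The consequence is a less relevant planning estimate. Its size cannot be computed: in the illustrations only the 16 + 16 patients come from the protocol, and every variance, recovery share, group difference and slope is assumed. Confidence is medium, because an analysis plan that is not shown could already close the gap.

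**What to change.** Replace the regression sentence in section 8 with wording such as:

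*Associations of MRI and CSF markers with cognitive decline will be examined by linear regression of the 12-month score on the marker, the baseline score of the same test and group (CAA/HA), primarily for the MMSE. The marker will be [its baseline level / its change over follow-up / each in turn]. Marker estimates will be reported separately for CAA and HA, with the difference between them (marker × group) and 95% confidence intervals, as descriptive estimates. As a sensitivity analysis the 3-month score will replace the baseline score.*

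The choice between the baseline and the 3-month reference is the sponsor's: the acute score carries deficits that may resolve, and the 3-month score misses earlier decline. The bracket must be filled because the objectives cover both marker level and progression. If a pooled estimate is wanted for the prediction model, it can be shown alongside, labelled as including the difference between diagnoses.

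The cost is wording and the loss of precision shown above. No new data are needed. The group-specific estimates and their difference will be too imprecise for more than description. CSF intervals will be wider still if some participants decline lumbar puncture: with 10 per group (an assumption), a within-group partial r of 0.30 has a 95% CI of about −0.45 to 0.80 (Fisher SE 1/√6).
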